#### Sodium nitrite and stable isotope labeled sodium N nitrite

Standard sodium nitrite will be supplied as capsules for daily oral administration at the dose strength of 20 mg (study dose: 20 mg). The Joint Food and Agriculture Organization (FAO)/World Health Organization (WHO) Expert Committee on Food Additives (JECFA) proposed an Acceptable Daily Intake (ADI) for sodium nitrite, which corresponds to 0.1 mg/kg of body weight. Using the ADI for sodium nitrite (0.1 mg/kg of body weight) and a body weight of 95 kg, the calculated ADI of sodium nitrite would be 9.5 mg. Much higher doses, of oral sodium nitrite solutions ranging between 140-380 mg are well tolerated acutely with minimal side effects characterized by short-term nausea and headaches, and mild transient reductions in blood pressure with concomitant increase in heart rate. Based on the Joint FAO/WHO ADI for nitrite, the fact that this dose has been approved by the FDA for studies in humans, it is believed that a safe and tolerated dose for sodium nitrite is 20 mg (~0.2 mg/kg body weight per day for a 95 kg subject). This dose selection is roughly equivalent to 2.1 times the ADI.

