#### Sodium nitrate and stable isotope labeled sodium N nitrate

Standard sodium nitrate will be supplied as capsules for daily oral administration at the dose strength of 500 mg (study dose: 1,000 mg). In a recent study, single dose potassium nitrate capsule ingestion in healthy adult volunteers in doses of 2,424 mg KNO3 (or 1,488 mg nitrate ion) and 1,212 mg KNO3 (or 744 mg nitrate ion) resulted in dose dependent reductions in BP over a 24 hour period without adverse effects (35). Current studies from this group are on-going with long term therapy for hypertension. Short term dietary supplementation with sodium nitrate at 0.1 mmol/kg of body weight per day divided up over 3 times daily for 3 days has been studied by Lundberg et al (36-38). The daily nitrate dose administered corresponds to the amount found in 100-300 grams of nitrate-rich vegetables such as spinach, beetroot or lettuce. Many of these studies demonstrated that dietary nitrate reduced systolic and diastolic blood pressures, mean arterial pressure (MAP), and oxygen cost during physical exercise and improved mitochondrial

efficiency without adverse effects. Several human studies have examined the effect of single ingestion (35, 39), 6 day(40, 41) and 15 day (42) supplemental courses of nitrate in the form of beetroot juice on blood pressure in healthy adults. Systolic (SBP), diastolic (DBP) and mean MAP were significantly reduced with beetroot juice in these trials with no adverse events noted (35, 39-42).

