**Potential Toxicity:** For nitrate, some toxicity studies suggest a positive association with risk of non-Hodgkin lymphoma, gastric and colon cancers with years of exposure. However, these were mostly studies with weak study design and limited strength of evidence. Other case-control studies and cohort studies, which provide stronger evidence, have found no increased risk of human cancer with increasing nitrate intake from diet or drinking water after multivariate adjustment. Taking all studies together, the CONTAM panel (Contaminants in the Food Chain) of the European Food Safety Authority (EFSA) reports evidence does not suggest that nitrate intake from diet or drinking water is associated with increased cancer risk (43). In addition, there is no clear evidence of an effect of nitrate or nitrite on non-cancer human health effects. In the current study, we will use much lower doses of nitrite and nitrate than used safely in any of these studies. Our sodium nitrate of 1gm represents a nitrate ion dose (i.e. 744 mg) that is less than the nitrate ion dose (i.e. 933 mg) associated with 1.488 gm of potassium nitrate used by Webb and colleagues. This medication will be provided by [name], under IND (115,926).

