### Run-In Period

The run-in period is from the time of consent (V1) to the first bronchoscopy (V3).

### Visit 1

- Sign consent form
- Review Inclusion and Exclusion criteria.
- Pre and post (4 puffs of albuterol) spirometry if patient has had adequate withhold (4 hours for SABA, 12 hours for LABA, 24 h for Tiotropium).
- Complete history and physical examination to include body weight, height, vital signs, waist and hip circumference
- Urine pregnancy test in females of child-bearing potential (i.e. women who are not at least 1 year post-menopausal or who have not undergone a surgical sterilization procedure).
- Exhaled NO. Niox mino. (No food, drink (other than water), or strenuous exercise 1 hour prior to visit)
- Asthma Control Test (ACT) and Asthma Control Questionnaire (ACQ)

### Visit 2

- Urine pregnancy test in females of child-bearing potential

- Exhaled nitric oxide test
- Brief physical exam
- Methacholine testing- This is a common test often used to confirm a diagnosis of asthma. Methacholine is a chemical that causes the airways to react (narrow) and is easily reversed with the administration of albuterol. Prior to the test, a urine pregnancy test will be performed on women of childbearing potential and a blood pressure reading will be taken. An exhaled nitric oxide test and a brief physical exam will also then be performed. The challenge test consists of inhaling very low, but increasing doses of methacholine through a nebulizer to assess how quickly the airways narrow. Spirometry (focusing on the FEV-1) will be performed approximately 30 and 90 seconds after each dose to look for changes in lung function. If/when a 20% decrease in spirometry (FEV-1) is observed the challenge test will be stopped. Multiple measures are in place to perform this test safely and comfortably. Subjects will receive albuterol after the test is done.
- If a subject's methacholine challenge test result is within 3% of what is positive (17% to 19% change), the participant can be re-tested within 14 days and enrolled accordingly (if 20% change or PC20 occurs). Additionally, if the subject's FEV1 is not 50% of predicted – participant can return within 7 days, and challenge can be done if pre-testing parameters are met. They can then continue with the study accordingly.

Visit 3 (Week 0) (Please see Bronchoscopy Procedure description below)

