### **Nitrite**

[name], a collaborator in this study, has previously held an IND for sodium nitrite (IND # 70,411) for cardiovascular applications and currently has an approved IND for the use of sodium nitrite for lung transplant recipients (IND # 111,643). The cardiovascular IND involved the administration of sodium nitrite to 69 normal volunteers in 4 phase I-II clinical trials without observed adverse effects. He has also treated 11 subjects with sickle cell disease on this IND without observed adverse effects. The low doses of nitrite used in these investigational treatment regimens – less than 75 mg or 25% of the dose (300mg) used in the emergency treatment of cyanide poisoning – do not produce methemoglobin levels greater than 3% and have not been associated with clinically significant hypotension. There have been no adverse events noted in the 80 treated normal human volunteers and patients with sickle cell disease (50-52). In another study by Gladwin et al., 18 healthy adults received an infusion of sodium nitrite totaling 75 mg (15 minutes each x 2 infusions). This was associated with a 7 mm Hg decrease in mean arterial pressure, a peak methemoglobin of less 3% and no other significant effects(51). Note this dose is 3.75 times the dose we plan to use in this trial.

In an open-label three-way crossover study, 9 healthy adult subjects received two single high dose oral sodium nitrite aqueous solutions (0.12 and 0.06 mmol NaNO2/mmol Hb, equivalent to 290-380 mg and 140-190 mg sodium nitrite, respectively, depending on the total body hemoglobin level of the person) and one intravenous sodium nitrite dose (0.12 mmol NaNO2/mmol Hb)(53). Mild headache occurred in 44-55% of subjects and was the most frequent complaint during each treatment session, which the authors ascribed to the sodium nitrite, not methemoglobinemia, as the percentage of methemoglobinemia stayed below clinically toxic levels (<15%). By report, up to 22% experienced nausea, which subsided within half an hour(53). The pharmacokinetic analysis of this study indicated similar bioavailability of oral and IV delivery of nitrite, as well as similar side effect and safety profiles.

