## **Nitrate**

For nitrate, some toxicity studies suggest a positive association with risk of non-Hodgkin lymphoma, gastric and colon cancers with years of exposure. However, these were mostly studies with weak study design and limited strength of evidence. Other case-control studies and cohort studies, which provide stronger evidence, have found no increased risk of human cancer with increasing nitrate intake from diet or drinking water after multivariate adjustment. Taking all studies together, the CONTAM panel (Contaminants in the Food Chain) of the European Food Safety Authority (EFSA) reports evidence does not suggest that nitrate intake from diet or drinking water is associated with increased cancer risk. In addition, there is no clear evidence of an effect of nitrate or nitrite on non-cancer human health effects(43).

In the current study, we will use much lower doses of nitrite and nitrate than used safely in any of these studies. Our sodium nitrite dose of 20 mg per day is <30% of the dose used on the cardiovascular IND and <7% of the dose used for cyanide poisoning. Our sodium nitrate of 1,000 mg represents a nitrate ion dose (i.e. 744 mg) that is less than the nitrate ion dose (i.e. 933 mg) associated with 1,488 mg of potassium nitrate used by Webb and colleagues(39). To summarize, We anticipate the following symptoms by organ system and likely frequency of risk during the 6 week treatment in this study:

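### The claim of much lower doses fits nitrite but not nitrate, and blood pressure is named only once on treatment and is absent from the safety analysis

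*Combined protocol and SAP*

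**What the plan says.** Section 5.3 (Potential Toxicity) and Section 9.1.2 (Nitrate) both state that "we will use much lower doses of nitrite and nitrate than used safely in any of these studies". Both then give the trial's 1,000 mg of sodium nitrate as 744 mg of nitrate ion, a figure "that is less than the nitrate ion dose (i.e. 933 mg") attributed to 1,488 mg of potassium nitrate in an earlier study.

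The sodium nitrate part of Section 5.3 cites:
- a single-dose potassium nitrate study in healthy adults, with arms of 1,488 mg ion and 744 mg ion. The text reads "or 744 mg nitrate ion) resulted in dose dependent reductions in BP over a 24 hour period without adverse effects";
- a regimen of "sodium nitrate at 0.1 mmol/kg of body weight per day divided up over 3 times daily for 3 days";
- beetroot juice as a single dose and as "6 day(40, 41) and 15 day (42) supplemental courses of nitrate", with no ion dose given.

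For nitrite, Section 5.3 says that oral doses of 140-380 mg produced "mild transient reductions in blood pressure with concomitant increase in heart rate". Section 9.1.2 describes 75 mg infused: "This was associated with a 7 mm Hg decrease in mean arterial pressure". The same section says that the low-dose regimens, under 75 mg, were not linked to clinically significant hypotension.

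On measurement, Section 6 includes vital signs in the Visit 1 examination. At Visit 2, before methacholine, "a blood pressure reading will be taken. An exhaled nitric oxide test and a brief physical exam will also then be performed". Visit 5 repeats this almost word for word. Visit 4 lists a short physical exam and Visit 6 a brief one, without naming blood pressure. Section 8.4 covers exacerbations, lung function and bronchial hyperresponsiveness.

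**The concern.** The dose rationale implies a wide margin below doses already tolerated, for both agents. If the nitrate margin is nil or small, the reassurance has to come from what was observed at the same dose. Those observations are short-term, come from healthy adults given nitrate without added nitrite, and include a fall in blood pressure. Section 3.1 makes safety and tolerability part of the primary hypothesis, and Section 9.1.2 lists hypotension among the rare drug risks. One would then expect the plan to collect and summarise blood pressure on treatment. As written, it names one such reading, at the end of the course, and no analysis of it.

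**Working it through.** **Inputs.** Trial: 1,000 mg sodium nitrate (printed as 744 mg ion) and 20 mg sodium nitrite daily for 8 weeks (Sections 1 and 5.3). Comparators as listed above. Body weight: 95 kg, the weight used in Section 5.3 for nitrite. Standard molar masses, not given in the protocol: nitrate ion 62.005, sodium nitrate 84.995, potassium nitrate 101.103.

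**1. Reproduce the printed ion doses.** Ion mg = salt mg × 62.005 / molar mass of the salt.

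| Salt | Computed ion | Printed ion |
|---|---|---|
| Sodium nitrate 1,000 mg (trial) | 729.5 mg | 744 mg |
| Potassium nitrate 1,212 mg | 743.3 mg | 744 mg |
| Potassium nitrate 2,424 mg | 1,486.6 mg | 1,488 mg |
| Potassium nitrate 1,488 mg | 912.6 mg | 933 mg |

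All agree within 3%, so the printed figures can be used.

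**2. Nitrate, trial divided by cited dose.**
- Lower potassium nitrate arm: 744/744 = 1.00 (by stoichiometry 729.5/743.3 = 0.98).
- Higher arm: 744/1,488 = 0.50 (0.49).
- The protocol's chosen comparator: 744/933 = 0.80 (0.80).
- The 0.1 mmol/kg/day regimen at 95 kg: 9.5 mmol × 84.995 = 807 mg sodium nitrate; 1,000/807 = 1.24. The doses are equal at 1,000/(0.1 × 84.995) = 117.7 kg, so the trial dose is the higher one for anyone lighter.
- Beetroot courses: cannot be compared, because no ion dose is given.

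**3. Nitrite.** 20/75 = 0.27; 20/140 = 0.14; 20/380 = 0.05. Here the claim holds.

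**4. Course length.** 8 weeks is 56 days; 56/15 = 3.7 times the longest nitrate course with a stated length. (Section 9.1.2 mentions 6 weeks in one place; that would give 42/15 = 2.8.)

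**5. Where blood pressure is named in Section 6.**

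| Contact | Blood pressure in the text |
|---|---|
| Visit 1, before treatment | Vital signs, within the examination |
| Visit 2, before treatment | Reading before methacholine |
| Visit 3, before first dose | Physical exam; not named |
| T1, week 2 | Phone call |
| Visit 4, week 4 | Short exam; not named |
| T2, week 6 | Phone call |
| Visit 5, week 8 | Reading before methacholine; no dose timing |
| Visit 6, 24 hours to 1 week later | Brief exam; not named |

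That is one of three on-treatment clinic visits (Visits 4, 5 and 6). The End of Study Visit for withdrawals does not name it either, so a participant who stops before week 8 could have no named on-treatment reading. At Visit 6 the last NOx dose is placed 24 hours before bronchoscopy in Section 5.2 and about 12 hours before in the Visit 5 instructions. A reading there needs its dose time recorded. It also needs to precede sedation, which Section 9.1.1 says can itself cause hypotension.

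**The case against.** **Which studies are meant is unclear.** In Section 5.3 the sentence directly follows the cancer and dietary-exposure studies. But the sentence after it compares the dose with a potassium nitrate dosing study, and Section 9.1.2 adds nitrite dosing comparisons, so the dosing studies are the natural reading. No intake figures are given for the exposure studies, so that reading cannot support the claim either. It is fair that the protocol prints both the 744 mg arm and the 933 mg comparator, so a careful reader can see the margin, and that no dose or analysis depends on the phrase.

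**The dose is unsafe.** A reader might infer this; the documents do not support it. The 744 mg arm is reported without adverse effects, and Section 5.3 equates the 0.1 mmol/kg/day regimen with 100-300 g of nitrate-rich vegetables. The nitrite-related falls came at 3.75 to 19 times the trial dose. Section 5.3 also mentions ongoing long-term nitrate studies, though without a length or result.

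**Blood pressure will not be measured at Visits 4 and 6.** This does not follow. The Visit 1 examination includes vital signs, so later exams may too. The separate listing at Visits 2 and 5 sits in repeated methacholine text that also re-lists the exam and exhaled NO, so it shows little about what an exam contains. Section 9.1.1 promises appropriate monitoring during bronchoscopy. What stands is that blood pressure is not named.

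**Falls would go unnoticed.** For symptomatic falls this is too strong. T1 and T2 ask about concerns and health care use, and Section 10.2 requires adverse events to be evaluated and followed, with DSMB review at least every 6 months. What stands is the gap for asymptomatic or mid-course falls.

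**Conclusion.** The concern holds in limited form, as a cheap improvement to the rationale and safety monitoring. The printed ion figures reproduce within 3%, so this is not an arithmetic error. The much-lower claim is right for nitrite (0.05 to 0.27 of the cited doses) and wrong for nitrate (1.00, 0.80 and 0.50 of the cited ion doses, and 1.24 times the weight-based regimen at 95 kg). The cited evidence supports short-term tolerability of this nitrate dose, not 8 weeks of both agents. The existing Visit 2 to Visit 5 pair could show a sustained fall at week 8, but without dose timing it is hard to interpret, and Section 8.4 plans no summary of it. This rests on reading the sentence as referring to the dosing studies, on 95 kg as a typical weight, and on the readable schedule being complete.

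**What to change.** 1. In Sections 5.3 and 9.1.2, limit the much-lower statement to nitrite. For nitrate, give the ratios and say that the cited courses with a stated length run to 15 days.
2. Record blood pressure and time since last dose at Visits 4 and 5, and at Visit 6 before sedation. Take a matching reading at Visit 3 before sedation, and so before the first dose.
3. At T1, ask directly about dizziness or light-headedness. The added readings will not detect a fall before week 4, and this question covers only symptomatic ones.
4. Add a paired summary of blood pressure before and on treatment to Section 8.4 and the DSMB report. With 12 participants planned it should be descriptive.

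The cost is a few minutes per visit, one question, one table and two edited sentences. Dose, sample size and efficacy analysis do not change. Whether to add a rule for withholding drug on low blood pressure is for the sponsor to decide.

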#### Conjugated Linoleic Acid

Will be supplied as capsules for daily oral administration at the dose of 3,000 mg/day from GNC. Conjugated linoleic acid (CLA) is a polyunsaturated fatty acid found in dairy products and ruminant meat (i.e. beef) and an average American diet supplies 15-174 mg of CLA daily. Moreover, CLA is formed in the body following conversion of linoleic acid to CLA by bacteria of the gastrointestinal tract. The predominant CLA species found clinically are octadeca-(9Z,11E)-dienoic acid and octadeca-(10E,12Z)-dienoic acid (44). Because linoleic acid cannot be synthesized in the body, it must come from the diet, as it is an essential fatty acid. Multiple clinical trials support that CLA promotes a broad range of physiological benefits (45). Additionally, previous reports demonstrated the ability of CLA to induce adipocyte lipolysis, fatty acid oxidation of adipocytes and significantly decrease body fat mass in obese and healthy overweight patients (33, 34). The benefits of CLA on inflammation have also been described, specifically through reducing macrophage-mediated infiltration into the adipose tissue and cytokine/leptin secretion, ultimately maintaining insulin sensitivity in a high-fat diet murine model of obesity (46). Furthermore, CLA

administration has been positively associated with reduced risk of colorectal cancer in human studies, and through animal studies, this effect was a result of reduced inflammation via PPAR $\gamma$  ligation (47, 48).

## **6 STUDY ASSESSMENT AND ORDER OF PROCEDURES**

### Pre-screening

- Based on an IRB-approved script, coordinators will pre-screen by phone or in person to determine if a potential participant should proceed to visit 1 based on major inclusion criteria such as asthma diagnosis, active smoking, presence of other lung diseases or exclusion criteria, etc.
- Participants that meet pre-screening criteria will be verbally consented to perform medication withhold to determine bronchodilator response.

### Run-In Period

The run-in period is from the time of consent (V1) to the first bronchoscopy (V3).

### Visit 1

- Sign consent form
- Review Inclusion and Exclusion criteria.
- Pre and post (4 puffs of albuterol) spirometry if patient has had adequate withhold (4 hours for SABA, 12 hours for LABA, 24 h for Tiotropium).
- Complete history and physical examination to include body weight, height, vital signs, waist and hip circumference
- Urine pregnancy test in females of child-bearing potential (i.e. women who are not at least 1 year post-menopausal or who have not undergone a surgical sterilization procedure).
- Exhaled NO. Niox mino. (No food, drink (other than water), or strenuous exercise 1 hour prior to visit)
- Asthma Control Test (ACT) and Asthma Control Questionnaire (ACQ)

### Visit 2

- Urine pregnancy test in females of child-bearing potential

- Exhaled nitric oxide test
- Brief physical exam
- Methacholine testing- This is a common test often used to confirm a diagnosis of asthma. Methacholine is a chemical that causes the airways to react (narrow) and is easily reversed with the administration of albuterol. Prior to the test, a urine pregnancy test will be performed on women of childbearing potential and a blood pressure reading will be taken. An exhaled nitric oxide test and a brief physical exam will also then be performed. The challenge test consists of inhaling very low, but increasing doses of methacholine through a nebulizer to assess how quickly the airways narrow. Spirometry (focusing on the FEV-1) will be performed approximately 30 and 90 seconds after each dose to look for changes in lung function. If/when a 20% decrease in spirometry (FEV-1) is observed the challenge test will be stopped. Multiple measures are in place to perform this test safely and comfortably. Subjects will receive albuterol after the test is done.
- If a subject's methacholine challenge test result is within 3% of what is positive (17% to 19% change), the participant can be re-tested within 14 days and enrolled accordingly (if 20% change or PC20 occurs). Additionally, if the subject's FEV1 is not 50% of predicted – participant can return within 7 days, and challenge can be done if pre-testing parameters are met. They can then continue with the study accordingly.

Visit 3 (Week 0) (Please see Bronchoscopy Procedure description below)

- The research coordinator will contact the subject 24-48 hours prior to Visit 3 in order to verify the medication withhold and readiness for the bronchoscopy procedure.
- Pt arrives to CTRC – MUH after an 8 hour fast
- Urine pregnancy test in females of child-bearing potential (i.e. women who are not at least 1 year post-menopausal or who have not undergone a surgical sterilization procedure).
- A physical exam will be completed
- The subject must have used less than 16 puffs of albuterol in the last 48 hours in order to proceed with bronchoscopy procedures
- Pre – bronchoscopy spirometry (pre- and post-bronchodilator) (safety assessment)
- Asthma Control Questionnaire (ACQ)& pre-bronchoscopy safety checklist
- Tongue scrape x microbiome
- Bronchoscopy for a) brushings , b) BAL, c) endobronchial biopsies; d) microbiome
- Blood work for metabolic syndrome ( fasting blood glucose, insulin levels, serum creatinine) lipid profile (HDL, triglycerides, total cholesterol, LDL and VLDL), CBC with differential, and Hgb A1C.

- Plasma collection
- Urine collection X Prostaglandin D2 (PGD2) metabolites and isoprostanes
- Exhaled NO (No food, drink (other than water), or strenuous exercise 1 hour prior to visit)
- Stool x microbiome
- Post bronchoscopy spirometry
- Dispense study drug supply- 4 week supply
- Distribute study Diary Card and review instructions

Phone call visit T1 (2 weeks after Visit 3)

- Review diaries & compliance
- ACQ
- Review any concerns and health care utilization

Visit 4 (4 weeks after Visit 3)

- Short Physical Exam
- Review of diaries and compliance
- Niox Mino (No food, drink (other than water), or strenuous exercise 1 hour prior to visit)
- Pre and Post spirometry
- ACQ & ACT
- Dispense 4 week supply of study drug

Visit 4A (if necessary)

If it is determined by the study coordinator at Visit 4 that the subject has not taken at least 75% of the study drug, the coordinator will provide a 1 week supply of the study drug and ask the subject to return to the Asthma Institute for a compliance check (visit 4A). If the subject is not compliant at Visit 4A, the subject will be withdrawn from the study. If the subject has improved compliance after 1 week, the remaining 3 week supply of the study drug will be dispensed.

Phone call visit T2 (6 weeks after Visit 3)

- Review diaries & compliance
- ACQ
- Review any concerns and health care utilization

